6.2 Study Population

In general, data such as patient disposition, demographics and baseline characteristics will be summarized for FAS_F population as the definition of FAS_F is identical to SAF_F if no patients were given wrong study drug. In the event when FAS_F is not identical to SAF_F then data will be summarized for both FAS_F and SAF_F as specified in the relevant sections.

6.2.1 Disposition of Subjects

Disposition of subjects will be summarized for the FAS_F by treatment group and overall. For the discontinuations, the primary reason reported by the investigator will be summarized.

Number and percentage of subjects for each analysis set will be summarized by treatment group and overall.

6.2.2 **Protocol Deviations**

The number and percentage of subjects with the following protocol deviation criteria will be summarized for the complete SAF population for each criterion and overall, by treatment group at the time the deviation occurs and total as well as by investigative site. Subjects deviating from a criterion more than once will be counted once for the corresponding criterion within a treatment group. The summary will include a column for PD during the 12-week placebo period. Placebo subjects deviating from a criterion while on placebo and again while on active treatment will be counted once in each treatment (e.g., placebo and fezolinetant) for the corresponding criterion, and the subject will be described in a footnote. However, such a subject would only be counted once in the Total column.

The listing will be based on the complete SAF population including all placebo data and subjects randomized to placebo who never received fezolinetant.

The unique identifiers will be as follows:

- PD1 Entered into the study even though they did not satisfy entry criteria,
- PD2 Developed withdrawal criteria during the study and was not withdrawn,
- PD3 Received wrong treatment or incorrect dose,
- PD4 Received excluded concomitant treatment.

The number of subjects who were affected by the COVID-19 pandemic will be summarized by impact item and treatment group and overall for SAF population. The impact items include treatment discontinuation, dosing change/interruption, death from COVID-19, healthcare encounter due to COVID-19, protocol deviation including missed visit windows due to COVID-19, and impacted diary data due to COVID-19.

An overview listing of subjects who were affected by the COVID-19 pandemic will be generated by the impact items.

Detailed information on how these assessments are affected by the COVID-19 pandemic can be found in relevant data listings with a flag for COVID-19.

6.2.3 Demographic and Other Baseline Characteristics

Demographics, tobacco history (smoking status), substance use (e-cigarette, alcohol, cannabis), caffeine beverage intake, height and weight, and targeted medical history will be summarized descriptively by treatment group and total group for FAS_F and SAF_F. Age group categories include <40 years, \geq 40 years to <46 years, \geq 46 years to <51 years, \geq 51 years to <56 years, \geq 56 years to <61 years, \geq 61 years to <66 years, and \geq 66 years. Note that current versus former or never smoking status is a stratification factor for randomization. Hormone replacement therapy history will be summarized descriptively by treatment group and total group for SAF_F.

Medical history is coded in MedDRA, and will be summarized by System Organ Class (SOC) and Preferred Term (PT) by treatment group and total group for the SAF_F.

These parameters will be summarized using the data collected at baseline.

6.2.4 **Previous and Concomitant Medications**

Previous and concomitant medications will be summarized by therapeutic subgroup (ATC 2nd level) and chemical subgroup (ATC 4th level) and preferred WHO name by treatment group for the FAS_F and SAF_F. Subjects taking the same medication multiple times will be counted once per medication and investigational period.

Previous medications are defined as medications that patients started prior to first administration of fezolinetant. Concomitant medications are defined as any medications that patients took after the first dose of fezolinetant and through 30 days from last dose of study drug. Medications that started prior to first administration of fezolinetant and continued while study drug was given will be counted in both previous and concomitant medications.

6.3 Study Drug Exposure and Compliance

Duration and compliance of study drug will be summarized for SAF_F by treatment group and overall.

Number and percentages of subjects with the following categories of study drug duration will be summarized: >0 to ≤ 1 day, >1 to ≤ 7 days, >7 to ≤ 14 days, >14 to ≤ 21 days, >21 to ≤ 28 days, >28 to ≤ 42 days, >42 to ≤ 56 days, >56 to ≤ 84 days, >84 to ≤ 112 days, >112 to ≤ 140 days, >140 to ≤ 168 days, >168 to ≤ 196 days, >196 to ≤ 224 days, >224 to ≤ 252 days, >252 to ≤ 280 days, >280 to ≤ 308 days, >308 to ≤ 336 days, >336 to ≤ 364 days, and >364 days.

Number and percentages of subjects with the following cumulative categories of study drug duration will be summarized: $\geq 1 \text{ day}$, $\geq 7 \text{ days}$, $\geq 14 \text{ days}$, $\geq 21 \text{ days}$, $\geq 28 \text{ days}$, $\geq 42 \text{ days}$, $\geq 56 \text{ days}$, $\geq 84 \text{ days}$, $\geq 112 \text{ days}$, $\geq 140 \text{ days}$, $\geq 168 \text{ days}$, $\geq 196 \text{ days}$, $\geq 224 \text{ days}$, $\geq 252 \text{ days}$, $\geq 280 \text{ days}$, $\geq 308 \text{ days}$, $\geq 336 \text{ days}$, and $\geq 364 \text{ days}$.

Overall treatment compliance with the dosing schedule will be examined for subjects in the SAF_F whose total study drug count and first and last days of treatment are known. Compliance will be calculated compared to the actual treatment period of dosing (first to last day of fezolinetant), not to the planned treatment period.

Percent overall compliance while on fezolinetant will be summarized in two ways for the SAF_F:

- Descriptive statistics will be presented by treatment group.
- Percent compliance will be categorized according to the following categories by treatment group:
 - Less than 50%,
 - at least 50%, less than or equal to 85%,
 - greater than 85%, less than or equal to 120%,
 - Over 120%, and
 - Unknown.

To explore the impact of the COVID-19 pandemic, additional analysis will be performed by excluding the days of missing study drug/drug interruption due to COVID-19 pandemic in the duration and compliance calculation, according to the study drug interruption CRF page.

6.4 Analysis of Efficacy

All efficacy endpoints will be descriptively summarized by the four treatment groups, as described in Section 6.1 (General Considerations), for FAS_F, unless specified otherwise.

For efficacy analyses, the visit windows from Section 6.10.1.1 and 6.10.1.2 will be applied, and they are all defined relative to the start of fezolinetant.

6.4.1 Analysis of Secondary Efficacy Endpoints

The mean change in the frequency and severity of moderate and severe VMS from baseline to week 24 will be summarized descriptively, as part of the output specified below and in Section 6.10.1.1.

The analysis will be repeated by excluding diary data that are impacted by COVID-19 pandemic, which includes the diary data recorded after the subjects were diagnosed of COVID-19, after study drug discontinuation due to COVID-19, and during dose interruption due to COVID-19.

6.4.2 Analysis of Exploratory Endpoints

The mean change in the frequency and severity of moderate and severe VMS from baseline to each analysis week up to week 12, and specified weeks thereafter (as specified in Section 6.10.1.1) will be summarized, including the secondary endpoint of Week 24.

For non-diary efficacy endpoints analysis visits are used rather than weeks, as described in Section 6.10.1.1.

PROMIS (SD and SRI total scores), MENQOL (domain and total scores), and WPAI-VMS domain scores will be summarized descriptively.

PGI-S and PGI-C (both VMS and SD) and EQ-5D domain scores will be summarized descriptively. The mean and standard deviation of the EQ-5D domain scores will be presented.

Change on the Euro-Qol 5D-5L (EQ-5D-5L) Visual Analog Scale (VAS) from baseline will be summarized descriptively.

The median change in serum concentrations of sex hormones and sex hormone-binding globulin (SHBG) from baseline to each analysis visit and the mean change in serum concentrations of BSAP, P1NP and CTX from baseline to each analysis visit will be summarized.

6.5 Analysis of Safety

All analysis of safety will be presented by the four treatment groups, as described in Section 6.1 (General Considerations), for SAF_F, unless specified otherwise. For analyses by visit, the visit windows from Section 6.10.1.2 will be applied, and they are all defined relative to the start of fezolinetant. Except for adverse events and follow-up visit data, only data up to one day after the last dose date will be considered for the analyses.

The baseline value for safety endpoint will be the last non-missing value taken on or prior to first dose of fezolinetant unless otherwise noted.

6.5.1 Adverse Events

TEAE is defined as an AE observed after starting administration of fezolinetant and up to 21 days after the last dose of study drug.

A study drug-related TEAE is defined as any TEAE with a causal relationship of YES by the investigator.

The sponsor has a list of events that they classify as "always serious" events. If an AE is reported that is considered by the sponsor to be an SAE per this classification as "always serious", the AE will be treated as an SAE in tables and listings, and flagged as 'always serious' in AE listings.

An overview table will include the following

- Number of TEAEs,
- Number and percentage of subjects with TEAEs,
- Number of drug related TEAEs,
- Number and percentage of subjects with drug related TEAEs,
- Number of serious TEAEs,
- Number and percentage of subjects with serious TEAEs,
- Number of serious drug related TEAEs,
- Number and percentage of subjects with serious drug related TEAEs,
- Number of TEAEs leading to permanent discontinuation of study drug,
- Number and percentage of subjects with TEAEs leading to permanent discontinuation of study drug, and
- Number of deaths.

The number and percentage of subjects with TEAEs in the following AE categories will be summarized for each treatment group by system organ class (SOC), high level term (HLT) and preferred term (PT):

- TEAEs
- drug related TEAEs.

The number and percentage of subjects with TEAEs in the following AE categories will be summarized by SOC and PT:

- serious TEAEs,
- drug related serious TEAEs,
- TEAEs leading to permanent discontinuation of study drug,
- drug related TEAEs leading to permanent discontinuation of study drug,
- TEAEs that equal to or exceed a threshold of 5.0% in any treatment group (threshold is based on PT).
- TEAEs excluding serious adverse events that equal to or exceed a threshold of 5.0% in any treatment group.

The number and percentage of subjects with TEAEs, as classified by PT only, will be summarized for each treatment group.

The number of TEAEs and the number and percentage of subjects with TEAEs, as classified by SOC and PT will be summarized by severity and by relationship to study drug. In the subject count, if a subject has multiple TEAEs with the same SOC or PT, but with differing severity or relationship, then the subject will be counted once with the worst severity and highest degree of relationship. If severity or relationship is missing for all episodes of the event, the subject will be counted under missing severity or relationship. In the adverse event count, the adverse events will be presented in each category they were classified to. Drug related TEAEs will be presented in a similar way by severity only.

Following adverse events of special interest are defined:

- Adverse event of uterine bleeding
- Endometrial hyperplasia/cancer or disordered proliferative endometrium
- Adverse event of thrombocytopenia
- Adverse event of liver test elevations
- Adverse event of bone fractures
- Adverse events of abuse liability
- Adverse events of depression
- Adverse events of wakefulness
- Adverse events of effect on memory

Search terms defining the AESIs will be pre-specified and documented.

The number and percentage of subjects with AESIs, as classified by PT will be separately summarized for each treatment group and listings of these adverse events will be provided.

The number and percentage of subjects with TEAEs associated with COVID-19, as classified by SOC and PT, will be summarized for each treatment group and overall.

6.5.2 Clinical Laboratory Evaluation

Quantitative values evaluated by the central laboratory including hematology, biochemistry, and urinalysis will be summarized using mean, standard deviation, minimum, maximum and median by treatment group at each analysis visit. Additionally, a within-subject change will be calculated as the post-baseline measurement minus the baseline measurement and summarized in the same way. Each laboratory result will be classified as low (L), normal (N), or high (H) at each visit according to the laboratory supplied reference ranges.

The number and percentage of subjects below and above reference range will be summarized for each treatment group at each visit.

Number and percentage of subjects with platelets $< 150000/\mu$ L ($150,000/\mu$ L ($150 \times 10^9/L$) will also be summarized.

Frequency tabulations of qualitative clinical laboratory variables (urinalysis) will be presented for each treatment group at each visit.

For hematology and biochemistry shift tables will be presented for each treatment group:

• Summary shifts of reference range changes from baseline to worst finding during the treatment period (shift from normal or high to low, shift from normal or low to high, categorized increase [shift from low to normal or from normal to high], categorized no change [value stays in the same reference range], categorized decrease [shift from high to normal or from normal to low]).

For hormone related parameters, if the value is below the low limit of quantification, the value will be imputed as half of the LLOQ. In addition, the percentage of subjects who have BLOQ values at baseline who then have measurable post-baseline values will be summarized.

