1.5 Risk Benefit Assessment

Fezolinetant is currently being developed for the treatment of VMS associated with the menopause (MR-VMS).

Based on recent advances in science, as well as the clinical data derived from 2 phase 2 clinical studies in women with VMS associated with the menopause, there are positive reasons to believe that fezolinetant can be an effective treatment for MR-VMS.

When given to normally cycling healthy women, fezolinetant is capable of altering the menstrual cycle and decreasing the circulating levels of E2, LH, progesterone (P4) and testosterone. Since this study aims to include menopausal women, these effects will be of less importance because of the physiological changes that happen in the climacterium (anovulation with loss of P4 and E2 production, and consequently increase of LH/FSH).

In terms of hormonal changes, a mild to moderate decrease of the already elevated LH and FSH plasma levels is anticipated. There are no known risks associated with this decrease of the gonadotropins in menopausal women.

Treatment with fezolinetant can cause adverse effects or other symptoms. Adverse effects that can be expected are those AEs that presented in fezolinetant clinical studies in healthy male and female volunteers, as well as in menopausal women.

Details of the AE profile from the completed clinical studies are presented in [Section 1.3 Fezolinetant Nonclinical and Clinical Data].

Across the completed phase 1 and 2a studies, there have been a small number of mild, transitory transaminase elevations observed both in patients/subjects who received either fezolinetant or placebo. There were no incidences of raised TBL and none of the patients/subjects experienced associated symptoms. In the recently completed phase 2b study ESN364_HF_205, transitory increases in transaminase enzymes, ALT/AST, have been reported in 7 subjects between 4 and 8 weeks after start of study treatment and in 2 unique subjects during study follow-up. Subjects were asymptomatic throughout and there was no evidence of functional liver impairment. Although there were cases with evidence of significant underlying hepatic conditions and other confounding factors, independent expert review concluded that the study drug was probably the cause of the increased transaminase levels. In all cases, transaminase enzyme levels rapidly decreased, in 2 cases during continuing treatment with study medication.

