6.7 Analysis of Pharmacodynamics

Serum concentrations of sex hormones (LH, FSH, E2, Testosterone Total/Free, Androstenedione, DHEA, Estrone) and SHBG will be summarized using descriptive statistics (number of subjects, mean, SD, median, minimum and maximum) for each analysis and for change from the baseline to each postdose visit, if the data is available.

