6.5.2 Clinical Laboratory Evaluation

Quantitative values evaluated by the central laboratory including hematology, biochemistry, and urinalysis will be summarized using mean, standard deviation, minimum, maximum and median by treatment group at each analysis visit. Additionally, a within-subject change will be calculated as the post-baseline measurement minus the baseline measurement and summarized in the same way. Each laboratory result will be classified as low (L), normal (N), or high (H) at each visit according to the laboratory supplied reference ranges.

The number and percentage of subjects below and above reference range will be summarized for each treatment group at each visit.

Number and percentage of subjects with platelets $< 150000/uL (150 \ 10^9/L)$ will also be summarized.

Frequency tabulations of qualitative clinical laboratory variables (urinalysis) will be presented for each treatment group at each visit.

For hematology and biochemistry shift tables will be presented for each treatment group:

• Summary shifts of reference range changes from baseline to worst finding during the treatment period (shift from normal or high to low, shift from normal or low to high, categorized increase [shift from low to normal or from normal to high], categorized no change [value stays in the same reference range], categorized decrease [shift from high to normal or from normal to low]).

For hormone related parameters, if the value is below the low limit of quantification, the value will be imputed as half of the LLOQ. In addition, the percentage of subjects who have BLOQ values at baseline who then have measurable post-baseline values will be summarized.

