6.7 Analysis of Pharmacodynamics

Serum concentrations of sex hormones (LH, FSH, E2, Testosterone Total/Free, Androstenedione, DHEA, Estrone) and SHBG will be summarized using descriptive statistics (number of subjects, mean, SD, median, minimum and maximum) for each visit and time point and for change from the baseline to each postdose visit, if the data is available

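### For hormones below the assay limit, both SAPs count only moves from unmeasurable to measurable; a two-way table by visit would show the offsetting falls (minor, descriptive output only)

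*SAP*

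**What the plan says.** Section 6.5.2 of both SAPs (52-week and 12-week) contains the same hormone rule: "if the value is below the low limit of quantification, the value will be imputed as half of the LLOQ". One categorical output follows: "the percentage of subjects who have BLOQ values at baseline who then have measurable post-baseline values will be summarized". Neither SAP says whether this is by visit or over all post-baseline visits, and neither makes the denominator explicit (all women, or women BLOQ at baseline). Neither plans a count of women who go from measurable to BLOQ.

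For hematology and biochemistry, the same section tabulates shifts in both directions: toward low, toward high, and no change of category.

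Two continuous summaries also cover hormones:

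- The exploratory analysis uses the median. In the 52-week SAP (6.4.2) it is: "The median change in serum concentrations of sex hormones and sex hormone-binding globulin (SHBG) from baseline to each analysis visit". Section 6.4.4 of the 12-week SAP does the same for weeks 4 and 12.
- Section 6.7 of the 52-week SAP covers every collected hormone and says that they "will be summarized using descriptive statistics (number of subjects, mean, SD, median, minimum and maximum) for each analysis and for change from the baseline". Section 6.7 of the 12-week SAP lists the same statistics "for each visit and time point and for change from the baseline to each postdose visit, if the data is available".

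**The concern.** A count of upward crossings alone is above zero whenever a hormone varies around the assay limit, even if nothing has changed on average. The matching downward crossings tell the reader that this is noise, and they are not shown. A figure for newly measurable estradiol, for example, could then be taken for a drug effect.

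The 52-week analysis makes this harder to detect. It has four groups, all on fezolinetant, plans no statistical comparisons (6.1), and drops post-baseline data from before the first fezolinetant dose (6.10.1), so no placebo percentage stands beside the active ones. If the sentence is programmed as any post-baseline value, the percentage also rises with the number of samples, which differs between the groups.

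**Working it through.** There is no figure in the plan to reproduce. The documents give no LLOQ values and no BLOQ shares, so all inputs to steps 1, 2 and 4 are assumptions.

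**1. Upward crossing at one visit with no true change.** Assume a standard bivariate normal scale with within-woman correlation ρ, a share p BLOQ at baseline, and c = Φ⁻¹(p). Among women BLOQ at baseline, the chance of being measurable at the visit is 1 − Φ₂(c, c; ρ)/p. At p = 50% this reduces to 1/2 − arcsin(ρ)/π.

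- ρ = 0.6: 0.5 − 0.6435/3.1416 = 29.5%
- ρ = 0.8: 0.5 − 0.9273/3.1416 = 20.5%

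| BLOQ at baseline | ρ = 0.6 | ρ = 0.8 |
|---|---|---|
| 30% | 42.4% | 29.6% |
| 50% | 29.5% | 20.5% |
| 70% | 18.2% | 12.7% |

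The range is about 13% to 42%. With no true change, the downward flow equals the upward flow as a share of all women. At p = 50% and ρ = 0.6, it is 0.5 × 29.5% = 14.8% each way. The plan shows only the upward one.

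**2. What a placebo column reveals.** For a true fall of 0.3 SD at p = 50%, the upward chance becomes 1 − Φ₂(c, c + 0.3; ρ)/p. That is 18.8% (ρ = 0.6) or 10.5% (ρ = 0.8), against 29.5% or 20.5% with no change. In the 12-week analysis this gap from placebo would be visible. In the 52-week analysis the 10.5% to 18.8% would stand alone and could be read as a rise.

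**3. Unequal numbers of visits.** Post-baseline hormone samples are scheduled at weeks 4, 12, 16, 24, 52 and 55 (Protocol 2.3.4 and Table 1 footnote q). For women who switch from placebo, the 52-week SAP (section 5) moves the hormone baseline to week 12, leaving weeks 16, 24, 52 and 55. So there are six visits against four. If the count means any post-baseline visit, with p = 50%, equal correlation between visits and no true change:

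- four visits: 59.5% (ρ = 0.6) or 41.8% (ρ = 0.8)
- six visits: 67.5% or 48.1%

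That is a gap of 8.0 or 6.3 percentage points from sampling alone. It disappears if the count is made by visit.

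**4. Do the continuous summaries fill the gap?** A woman BLOQ at both visits gets LLOQ/2 − LLOQ/2 = 0. If more than half of women are in that state, the median change is exactly 0 whatever the rest do. An illustrative simulation gives change in LLOQ units (400,000 women, lognormal values, log-SD 0.6, ρ = 0.7, true fall of 30%):

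| BLOQ at baseline | Mean: true / imputed | Median: true / imputed |
|---|---|---|
| 20% | −0.60 / −0.62 | −0.44 / −0.54 |
| 40% | −0.42 / −0.41 | −0.31 / −0.07 |
| 60% | −0.31 / −0.26 | −0.23 / 0.00 |

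The mean still shows the fall. The median is distorted and, in the 60% case, hides it. In that case 3.5% of all women cross upward, which would be counted, and 23.6% cross downward, which would not.

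**The case against.** A reader might infer that the hormone tables can show only rises, so that the pharmacodynamic objective cannot be answered. The documents do not support this. Section 6.7 of both SAPs, and Protocol 7.7, summarize mean, SD, median, minimum and maximum change. A move from measurable to BLOQ enters these as a negative change through the half-LLOQ value. The one-way reading applies only to the single added percentage.

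A reader might also infer that the uncounted direction is the one the protocol's pharmacology predicts. Protocol 1.5 does say that "fezolinetant is capable of altering the menstrual cycle and decreasing the circulating levels of E2, LH, progesterone (P4) and testosterone", but of normally cycling women, and it gives these effects less weight after menopause. The fall it anticipates in this population is in LH and FSH, which are already elevated and should seldom lie near an assay limit. Progesterone is not collected. For estradiol and androgens in these women, the documents forecast no fall.

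Three further points stand:

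- The sentence sits under safety, so it may be meant as a screen for rises, although neither SAP says so.
- The 12-week analysis has concurrent placebo and the same two hormone visits (weeks 4 and 12) in every arm.
- The any-visit figures depend on a rule that the SAPs do not state; nearby laboratory counts are by visit.

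None of this explains why the downward flow is omitted. A two-way table would serve a screen for rises equally well.

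**Conclusion.** The point holds as a minor reporting gap. Both SAPs count crossings of the assay limit in one direction only. Under the assumed inputs, about 13% to 42% of BLOQ women would be counted at one visit with no true change. The 52-week analysis has neither a placebo column nor a downward count to put this in context, and the median endpoint does not help where BLOQ is common.

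The size rests wholly on the assumed BLOQ share and correlation. The issue is confined to hormones that are often near the limit, possibly estradiol or some androgens; for LH and FSH it should be negligible. All affected output is descriptive. The co-primary and key secondary analyses, alpha and sample size are untouched.

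**What to change.** In 6.5.2 of both SAPs, replace the sentence with a two-way table for each hormone: BLOQ or measurable at baseline against BLOQ or measurable at the visit, by visit and treatment group, with the denominator stated as women with both values. Where more than 50% of women are BLOQ at baseline, also report the proportion measurable at each visit alongside the half-LLOQ change summaries. Tabulating by visit settles the unstated time rule and removes the effect of six visits against four.

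The cost is a wording change and one small table per hormone. No new data are needed.
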